10.2.3. Ophthalmoscopy

Dilated ophthalmoscopy should be performed as part of each ophthalmic examination at every office visit. This procedure should be the same for all patients examined at the site and use the same equipment. Significant clinical abnormalities which develop during the study should be

recorded as an adverse event. All findings are to be documented in the source documentation and the appropriate CRF.

10.2.4. Visual Acuity

Visual acuity assessment should be performed using standard ETDRS charts or the investigator's standard procedure. Patients should be tested with their own (if any) habitual spectacle correction. The same procedure should be performed at every office visit. (All visual acuity assessments will be converted to ETDRS letter scores for data analysis.)

10.2.5. Intraocular Pressure

IOP measurements will be recorded using the investigator's standard procedure at every office visit. The same procedure should be performed at every office visit.

10.3. Unscheduled Visits

In the event that the patient's vision deteriorates between scheduled study visits, the patient should have an unscheduled visit. In addition to the assessments necessary to evaluate the cause of the vision loss, information on AEs, concomitant medications and any treatment required, should be obtained. An unscheduled visit evaluation form should be completed.

11. EVALUATION, RECORDING AND REPORTING OF ADVERSE EVENTS

All adverse events either observed by the investigator or site staff, or reported by the patient spontaneously, or in response to the direct question below, will be noted in the adverse events section of the patient's CRF and/or in the source document. Only treatment-emergent adverse events (those occurring during or after the start of ILUVIEN treatment) should be recorded as adverse events. Events reported before the initial ILUVIEN treatment should be recorded as medical history. For serious adverse events (SAEs) however, any SAE occurring after the patient has been consented will be recorded and reported as an SAE to Alimera within 24 hours.

In an attempt to optimize consistency of adverse event reporting, the patient should be asked a standard question to elicit any adverse events. At each clinic or telephone evaluation of the patient, study personnel will ask the following question: "Have you had any problems since your last visit or telephone call?"

If any adverse event is reported, the date of onset, intensity, action taken, relationship to study medication or treatment, date of resolution (or the fact that it is still continuing or has become chronic) and whether the adverse event is serious or not will be recorded (see Section 11.3.1).

To prevent duplicate reporting, please report AEs or SAEs to the registry study in lieu of report to a health authority. The sponsor has the responsibility to report relevant events to the appropriate health authority.

If a patient is enrolled retrospectively, then the investigator should add into the CRF all adverse events noted in the source documents which occurred after treatment with ILUVIEN and prior to the patient providing informed consent for this study.

11.1. Definitions

11.1.1. Adverse Event

An AE is any unfavorable and unintended sign (including a clinically significant abnormal laboratory finding), symptom, or disease temporally associated with the administration of a medicinal product, whether or not considered related to the investigational product.

Medical conditions or diseases present before a patient starts study treatment are only considered AEs if they worsen after the patient starts study treatment.

An example of a non-serious adverse event would be conjunctival hemorrhage following administration of ILUVIEN.

11.1.2. Serious Adverse Events

Serious Adverse Event is defined as any AE that:

- Results in death
- Is life-threatening (The term "life-threatening" refers to an event in which the patient was at risk of death at the time of the event; it does not refer to an event which hypothetically might have caused death if it were more intense.)
- Requires inpatient hospitalization or prolongs existing hospitalization

- Results in persistent or significant disability / incapacity
- Is a congenital anomaly / birth defect
- May jeopardize the patient or may require intervention to prevent one of the
 outcomes listed above. Medical and scientific judgment should be exercised in
 deciding if these events should be considered serious. Examples of such events are
 intensive treatment in an emergency room or at home for allergic bronchospasm;
 blood dyscrasias or convulsions that do not result in hospitalization; or development
 of drug dependency or drug abuse.

A patient admitted to a hospital as a result of an AE, even if released on the same day, would qualify for inpatient hospitalization. An emergency room visit that results in admission to the hospital would also qualify for inpatient hospitalization. However, emergency room visits that do not result in admission to the hospital would not qualify for inpatient hospitalization and, instead, should be evaluated for one of the other criteria for SAEs (e.g., life-threatening AE or medically significant event).

Surgery or hospitalization should always be reported as an outcome of an AE. Disability/incapacity refers to a substantial disruption of a patient's ability to carry out normal life functions.

11.2. Adverse Event Descriptions

11.2.1. Intensity

The intensity of AEs will be characterized as mild, moderate, or severe, as follows:

Mild Usually transient, requiring no special treatment, and does not

interfere with the patient's daily activities

Moderate Introduces a low level of inconvenience or concern to the patient

and may interfere with daily activities, but is usually ameliorated

by simple therapeutic measures

Severe Significantly interferes with a patient's usual daily activities and

requires systemic drug therapy or other treatment, if available

11.2.2. Relationship to Study Treatment

The causal relationship to study drug or treatment will be determined by the investigator according to best medical judgment, as follows:

Suspected There is a reasonable possibility that the AE is associated with use

of the study treatment, such as a temporal relationship of the event to study treatment administration, or when other drugs, therapeutic interventions, or underlying conditions do not provide a sufficient

explanation for the observed event.

Not suspected A relationship between the AE and the study treatment can

reasonably be ruled out based on lack of any temporal relationship of the event to study treatment administration, or when the patient's underlying condition, medical history, or other therapy provide

sufficient explanation for the observed event.

11.3. Reporting and Evaluation of Serious Adverse Events and Other Clinically Significant Adverse Events

11.3.1. Serious Adverse Events

Any SAE occurring in this study must be reported immediately (within 24 hours) to the sponsor safety contact using the SAE Form provided by the sponsor.

Patients enrolled retrospectively may have experienced an SAE after ILUVIEN administration but prior to providing informed consent for the study. These "retrospective" SAEs should be reported to the sponsor, via the SAE form, as soon as possible after the patient has provided informed consent for the study.

The investigator or sponsor, if appropriate, must also submit documentation of the following to the Ethics Committee (EC):

Center-specific SAEs and follow-up to these SAEs: The type of SAE that must be submitted (e.g., all SAEs or only suspected SAEs), as well as the required timing of submission (e.g., within 15 days of occurrence), is defined by the EC or regulatory authorities.

All reportable SAEs from the study: The sponsor will provide the investigator with documentation of reportable SAEs, from all study centers, during the conduct of the study.

The investigator should ensure that the patient receives appropriate medical treatment and that the patient is followed up until the SAE resolves or becomes chronic, as defined in Section 11.5.

11.3.2. Other Clinically Significant Adverse Events

Serious ocular adverse events include the following:

• Any ocular surgical intervention (e.g., cataract surgery, glaucoma surgery).

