2. INTRODUCTION

ILUVIEN 190 micrograms intravitreal implant in applicator is a sustained-release intravitreal drug delivery system that releases submicrogram levels of the corticosteroid, fluocinolone acetonide (FAc), in the vitreous humor for approximately 36 months. The product was first approved in selected countries in the European Union in the second quarter of 2012. The approved indication is:

"ILUVIEN is indicated for treatment of vision impairment associated with chronic diabetic macular oedema considered insufficiently responsive to available therapies."

The efficacy of ILUVIEN was assessed in two randomized, multicenter, double-masked, parallel studies enrolling subjects with diabetic macular oedema who had previously been treated with laser photocoagulation at least once, each involving three years of follow-up (the FAME studies). The primary efficacy endpoint, the proportion of subjects whose vision improved by 15 ETDRS letters or greater at Month 24 was statistically significantly greater in subjects treated with ILUVIEN than the sham control group. (Campochiaro *et al* 2012) When efficacy was assessed as a function of duration of disease, those subjects with duration of diabetic macular oedema (DMO) greater than the median (≥3 years) had a significant beneficial response to ILUVIEN, whilst those with shorter duration DMO did not show an additional benefit over sham control treatment with regard to visual improvement (Figure 1).

Figure 1: Comparison of Percent of Subjects with ≥15 letter Improvement from Baseline Best Corrected Visual Acuity in Subjects with Chronic DMO

The main safety findings from the FAME studies were that essentially all phakic subjects treated with ILUVIEN experienced development of, or progression of, cataract and required cataract surgery. The proportion of ILUVIEN-treated subjects requiring treatment with intraocular pressure lowering medication was 38% compared to 14% in the sham-treated group. This proportion increased to 47% in those subjects with greater than average IOP at baseline (>15

mmHg). Surgical interventions for the treatment of ocular hypertension were required in 4.8% of subjects treated with ILUVIEN compared to 0.5% of subjects treated with sham control. Therefore, ILUVIEN should be used with caution in patients with high baseline IOP, and IOP must be monitored closely.

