11.4. Events Due to Disease Progression

Events that are judged to be definitely due to disease progression should be recorded in the source documents, but not reported as AEs.

However, events that meet the criteria for SAEs (as defined in Section 11.1.2) even though they are judged definitely due to disease progression should be reported as SAEs (as described in Section 11.3.1).

The unequivocal nature of the disease progression must be indicated in the source documents.

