11.5. Follow-up for Adverse Events

Throughout the study to the final study visit, all AEs will be followed until they resolve or become chronic (as judged by the investigator).

At the final study visit, new AEs, as well as follow-up information for continuing AEs, will be recorded in the CRF and source document. Beyond the final study visit, AEs will be followed only until 30 days after the final study treatment.

If a serious AE (defined in Section 11.3) is unresolved within 30 days after the final study visit, it will be followed by the investigator until it resolves or becomes chronic (as judged by the investigator). Follow-up data for such SAEs will be recorded on the CRF and source documents and reported to the safety contacts until the event resolves or becomes chronic (as judged by the investigator) or until 30 days after the final study visit, whichever comes first.

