12.5. Safety Variables

Safety analyses will be performed on all patients who receive ILUVIEN. Ocular safety will be assessed by evaluating ocular adverse events, retreatments with ILUVIEN, visual acuity, intraocular pressure, and concomitant ocular medications and therapies. If a patient receives bilateral ILUVIEN, then each eye will be summarized.

Systemic safety will be assessed by evaluating non-ocular adverse events, and concomitant non-ocular medications and therapies.

Adverse events will be summarized by presenting the number and percentage of patients having at least one occurrence of any adverse event during the study, having at least one occurrence of an adverse event within each system organ class, and having at least one occurrence of each individual adverse event. Each reported adverse event will be coded to a corresponding preferred term from the MedDRA coding dictionary.

For continuous safety variables, e.g., visual acuity, intraocular pressure, the observed and change from baseline values will be summarized descriptively (n, mean, standard error, standard deviation, median, minimum, maximum and frequency distribution) at each visit.

Specific adverse events of interest will be tabulated: IOP-related and cataract-related events, procedural complications such as endophthalmitis, retinal tears, retinal detachments, vitreous

haemorrhage or vitreous detachments. Potential safety risks that have not been observed in clinical trials will also be monitored such as, retinitis secondary to reactivation of latent viral infections or other ophthalmic infections, potential systemic events associated with the use of corticosteroids or haemorrhagic events associated with the concurrent therapy with anticoagulant medications. Information on retinal ischaemia, removal of the implant, and long-term safety data will be evaluated.

An evaluation of safety in patients who have received ILUVIEN in both eyes during the study will also be performed.

Summaries for specific subgroups of patients will be performed on all safety data. Analyses will be performed to determine the effect of treatment within specific subgroups of interest. Subgroups to be considered include:

- Patients diagnosed with diabetic macular oedema for 3 or more years
- Patients diagnosed with diabetic macular oedema for less than 3 years
- Patients not diagnosed with diabetic macular oedema
- Patients receiving a single ILUVIEN during the study

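### Ocular surgery is the outcome of an AE in Section 11.1.2 but is listed as a serious ocular AE in Section 11.3.2, and Sections 11.4 and 11.5 cite different SAE definitions

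*Protocol*

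**What the plan says.** Section 11.1.2 defines an SAE by the usual general criteria and adds a recording rule: "Surgery or hospitalization should always be reported as an outcome of an AE". On admission it is broad: "A patient admitted to a hospital as a result of an AE, even if released on the same day, would qualify for inpatient hospitalization". It also has a judgement criterion for events that may need intervention to avert a listed outcome. Ocular surgery is not among its criteria.

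Section 11.3.2 stands under a heading about other clinically significant events, separate from the SAE section before it. It opens with "Serious ocular adverse events include the following" and has a single entry: "Any ocular surgical intervention (e.g., cataract surgery, glaucoma surgery".

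Two later sections point to different definitions. Section 11.4 keeps events attributed with certainty to disease progression out of AE reporting, except "events that meet the criteria for SAEs (as defined in Section 11.1.2". Section 11.5 sets follow-up with the words "If a serious AE (defined in Section 11.3) is unresolved within 30 days after the final study visit", and Section 11.3 contains 11.3.2.

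Section 12.5 counts patients with any AE, with an AE in each system organ class, and "having at least one occurrence of each individual adverse event". It also tabulates IOP-related and cataract-related events. The Introduction reports from the earlier randomised studies that "essentially all phakic subjects treated with ILUVIEN experienced development of, or progression of, cataract and required cataract surgery", and that 4.8% of treated subjects needed surgery for ocular hypertension.

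**The concern.** In one section the operation is what happened because of an adverse event; in the other it is the adverse event. A site following 11.1.2 enters cataract, with surgery as the outcome. A site following 11.3.2 literally enters cataract surgery. A cautious site may enter both. A diagnosis and an operation are different entries in a table of individual terms and can fall under different system organ classes, so these counts would partly reflect site habit across about 45 centres.

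Cataract and raised IOP lead the known risks in the study objectives, and ocular surgery is expected to be common. Seriousness also matters operationally: it triggers the 24-hour report and Ethics Committee documentation (11.3.1) and the longer follow-up (11.5). What a site writes as the event, and whether it marks it serious, is settled at data entry. An analysis plan can group terms afterwards, but it cannot restore a report that was never made.

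**Working it through.** **The plan's own figure.** Section 12.1 gives about 80% probability of at least one report of an event with 0.3% incidence in 550 patients. Check: 1 − (1 − 0.003)^550 = 0.808. It reproduces, and this point does not affect it.

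**The passages side by side.**

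| Situation | Under 11.1.2 (and 11.4) | Under 11.3.2 (and 11.5) |
|---|---|---|
| Cataract develops and is operated on | Event is cataract; surgery is its outcome | Surgery is itself listed as the event |
| Seriousness, no admission | Not automatic; the judgement criterion may apply | Always serious |
| Seriousness, with admission | Serious, even if released the same day | Serious |
| Surgery for a cataract present at baseline that has not worsened | No AE exists (11.1.1), so there is nothing for surgery to be the outcome of | Serious ocular AE |
| Surgery without admission for an event attributed to disease progression | Not reportable unless another 11.1.2 criterion is met | Serious ocular AE |

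**How many patients are exposed.**

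- IOP surgery: 550 × 0.048 = 26.4, about 26 patients, if the rate in the Introduction carries over.
- Cataract surgery: the protocol does not give the phakic share. I assume 20%, 40% or 60%, with every phakic patient operated on: 550 × 0.20 = 110, 550 × 0.40 = 220, 550 × 0.60 = 330.

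**Effect on the share of patients with an SAE.** If 11.3.2 is applied, all operated patients count, whether the entry reads cataract or cataract surgery, so the choice of term alone changes nothing. If 11.3.2 is ignored and only admission makes a case serious, the difference is phakic share × (1 − admitted share). The admitted share is also assumed:

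| Phakic share | Operated, of 550 | 0% admitted | 50% admitted | 100% admitted |
|---|---|---|---|---|
| 20% | 110 | 20 points | 10 points | 0 |
| 40% | 220 | 40 points | 20 points | 0 |
| 60% | 330 | 60 points | 30 points | 0 |

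For example, 0.40 × (1 − 0.50) = 0.20, or 20 points. The non-zero cells are ceilings for their row and column. They assume that no investigator uses the judgement criterion, that no operated patient has another SAE, and that all phakic patients have surgery. The last is carried over from studies with three years of follow-up, whereas this registry has varying follow-up and accepts any indication.

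**The case against.** The strongest reply is that the two sections are compatible. The surgery sentence in 11.1.2 is a recording rule and never calls such events non-serious. If 11.3.2 is read as a seriousness criterion, cataract is the AE, surgery its outcome, and the event serious. A non-serious operated cataract then arises only where a site fails to apply 11.3.2. This is a sensible reading and the one the fix writes down. But the protocol does not state it, the wording of 11.3.2 names the operation as the event, and the reading does not settle which definition Section 11.4 means.

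Second, Section 10.2.2 already has significant abnormalities found at slit lamp recorded as AEs, so a developing cataract should appear in its own right whatever is written for the operation. Counting each patient once limits inflation from double entry. The cataract-related and IOP-related groupings may also pool diagnosis and procedure terms; their definition may properly sit in a SAP that is not shown. All of this stands, and it confines the damage mainly to the individual-term and system organ class tables.

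A reader might infer that the cataract term would lose up to half its surgical cases if half the sites entered the procedure. Section 10.2.2 is the reason the protocol does not support that.

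**Conclusion.** The inconsistency is real and worth correcting. Two sections give different instructions on what the event is, and two others rely on different SAE definitions. What follows with confidence is inconsistent term-level and system organ class counts for the main known risks, and uncertain reportability of progression-related surgery without admission.

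A reader might infer more: that the sections disagree outright on seriousness, or that the SAE rate will shift by tens of percentage points. The protocol does not support either. Section 11.1.2 does not call surgical cases non-serious, and the shift is anywhere from zero upwards, depending on phakic share, admission practice and adherence to 11.3.2, none of which the document gives. The upper values need 11.3.2 to be disregarded and no other criterion to apply. The only count resting on a rate in the protocol is about 26 of 550 for IOP surgery, and it shows how many patients are exposed to the ambiguity, not how many would be misclassified.

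**What to change.** Reconcile 11.1.2 and 11.3.2 with one recording rule: the underlying condition in the treated eye is the AE term, the surgery is its outcome, and 11.3.2 is stated to be a seriousness criterion for AEs that lead to ocular surgery. The rule should also say how surgery with no AE behind it is recorded. Make 11.4 and 11.5 cite the same SAE definition, so that the handling of progression-related surgery is explicit.

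Tabulate cataract and glaucoma surgery rates from the ocular-procedures data, which the Synopsis already lists among the study procedures, rather than from AE terms. Those rates then do not depend on how a site worded the event.

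The cost is one protocol paragraph, matching text in the CRF instructions, and a query round for events already entered. The sample size is unchanged.

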11.4. Events Due to Disease Progression

Events that are judged to be definitely due to disease progression should be recorded in the source documents, but not reported as AEs.

However, events that meet the criteria for SAEs (as defined in Section 11.1.2) even though they are judged definitely due to disease progression should be reported as SAEs (as described in Section 11.3.1).

The unequivocal nature of the disease progression must be indicated in the source documents.

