4. STUDY OBJECTIVES AND PURPOSE

The study will assess the safety and usage in patients treated with ILUVIEN.

The specific objectives include the study of known safety risks of cataract formation or progression, increased intraocular pressure (both within 30 minutes post-treatment and long-term), changes in intraocular pressure and development of glaucoma, procedural complications such as endophthalmitis, retinal tears, retinal detachments, vitreous haemorrhage or vitreous detachments. Potential safety risks that have not been observed in clinical trials will also be monitored such as, retinitis secondary to reactivation of latent viral infections or other ophthalmic infections, potential systemic events associated with the use of corticosteroids or haemorrhagic events associated with the concurrent therapy with anticoagulant medications. Unknown safety risks will be captured as well. Information on significant retinal ischaemia, removal of the implant, long-term safety data, and repeat use will be evaluated. An evaluation of safety in patients who have received ILUVIEN in both eyes during the study will also be performed. The change from baseline visual acuity (VA) will be evaluated.

Any use in paediatric patients, pregnant or lactating women and off-label use for other retinal oedema conditions will be reported. It should be understood that the sponsor does not advocate the use of ILUVIEN for any indication other than that which is specified on the Summary of Product Characteristics (SPC). However, it is also known that, in clinical practice with marketed products, off-label use is common. Therefore, the sponsor intends to collect safety data of any patient treated with ILUVIEN.

This study will collect data for 6.5 years from the date of enrolment of the first prospectively enrolled patient. As a result, patients will have varying numbers of study visits.

Amendment 1 to this protocol allows for the retrospective enrollment of patients treated with ILUVIEN prior to enrolment into the study provided that they satisfy the same entry criteria as applied to patients enrolled prospectively.

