10.2.2. Slit Lamp Examination

Slit lamp examination should be performed at every office visit in the study using the investigator's standard procedure. This procedure should be the same for all patients examined at the site and use the same equipment. Significant clinical abnormalities which develop during the study should be recorded as an adverse event. All findings are to be documented in the source documentation and the appropriate CRF.

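### Section 11.4 withholds non-serious events attributed to disease progression from adverse event reporting, contradicting Sections 11.1.1, 10.2.2 and 10.2.3

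*Protocol*

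**What the plan says.** Section 11.4 sets the reporting rule for progression: "Events that are judged to be definitely due to disease progression should be recorded in the source documents, but not reported as AEs". It keeps one group reportable, namely "events that meet the criteria for SAEs (as defined in Section 11.1.2) even though they are judged definitely due to disease progression". It also asks that the source documents show the progression to be unequivocal.

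Three other places bear on the same events:

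- **Section 11.1.1** includes in its definition of an adverse event any "symptom, or disease temporally associated with the administration of a medicinal product, whether or not considered related to the investigational product". On existing disease it says: "Medical conditions or diseases present before a patient starts study treatment are only considered AEs if they worsen after the patient starts study treatment".
- **Section 10.2.2** (slit lamp) says: "Significant clinical abnormalities which develop during the study should be recorded as an adverse event". Section 10.2.3 repeats this for dilated ophthalmoscopy. Neither makes an exception for progression, and both also send all findings to the CRF.
- **Section 11.2.2** already lets the investigator class an adverse event as not suspected to be related when the underlying condition explains it.

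Among the objectives, Section 4 states: "Information on significant retinal ischaemia, removal of the implant, long-term safety data, and repeat use will be evaluated". Sections 4 and 12.5 also name vitreous haemorrhage, retinal tear, retinal detachment and vitreous detachment, as examples of procedural complications. The incidence summaries in Section 12.5 give numbers and percentages of patients with adverse events.

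**The concern.** Attribution to the underlying disease is a causality judgement. Under Sections 11.1.1 and 11.2.2 that judgement labels an adverse event and does not decide whether it is one. Under Section 11.4 the same judgement takes a non-serious event out of adverse event reporting altogether.

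This matters because of what the study is for. It is a safety registry requested by the regulator (Section 3), with no control group (Section 5.1) against which background progression could be judged. Some of the events it is meant to examine can also arise from the disease under treatment. Section 11.4 does not say which disease is meant or what makes progression definite, although any treated patient may enrol (Section 6.2) and Section 12.5 foresees diagnoses other than diabetic macular oedema. Sites may therefore apply the rule differently, and its effect may differ between the diagnosis subgroups that Section 12.5 will summarise.

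**Working it through.** **1. One case under each rule.** A patient has a new, non-serious area of retinal ischaemia on dilated ophthalmoscopy after implantation. The investigator is sure that it is due to diabetes.

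| Section | Instruction for this event |
|---|---|
| 10.2.3 | If clinically significant, record as an adverse event |
| 11.1.1 | Adverse event, since existing disease worsened; cause does not matter |
| 11.2.2 | Relationship: not suspected (still an adverse event) |
| 11.4 | Source documents only; not an adverse event |

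The last row cannot be followed together with the others.

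**2. Which events are affected.**

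- Only non-serious events, because of the exception in Section 11.4.
- Only those judged definitely due to progression. Doubtful or mixed attributions stay adverse events.
- Chiefly retinal ischaemia and worsening retinal disease. Vitreous haemorrhage, tear or detachment is affected only where it is attributed to the disease and not to the procedure.

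**3. The seriousness exception.** It cites Section 11.1.2 only. Section 11.3.2 classes any ocular surgical intervention as a serious ocular event, and Section 11.5 refers to Section 11.3 for the definition of a serious event. The text does not settle whether a progression event leading to ocular surgery is kept.

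**4. The plan's own figure.** Section 12.1 gives 550 patients, a true 5-year incidence p = 0.3%, and about 80% probability of one or more reports.

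P(at least one report) = 1 − (1 − p)^n = 1 − (1 − 0.003)^550 = 0.808.

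The stated 80% is reproduced. The significance level quoted with it plays no part in this formula. The calculation presumes that every patient with the event is reported.

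**5. Illustration of the effect.** Let f be the share of affected patients whose event is withheld under Section 11.4. The protocol gives no value for f, so the values below are assumptions. Take an event type that is entirely non-serious, with p = 0.3%. The reported incidence is p(1 − f), and

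P(at least one report) = 1 − (1 − p(1 − f))^550.

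The true incidence needed for an 80% chance of one report is (1 − 0.2^(1/550))/(1 − f) = 0.292%/(1 − f).

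| f (assumed) | Reported incidence | P(at least one report) | True incidence needed for 80% |
|---|---|---|---|
| 0% | 0.300% | 80.8% | 0.29% |
| 10% | 0.270% | 77.4% | 0.32% |
| 25% | 0.225% | 71.0% | 0.39% |
| 50% | 0.150% | 56.2% | 0.58% |
| 75% | 0.075% | 33.8% | 1.17% |

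For commoner events the effect is simple proportion: the tabulated percentage is the true one times (1 − f).

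**The case against.** The best defence is that Section 11.4 is a deliberate, specific exception to a general definition. It keeps serious events, sets a high threshold and requires documentation, so the judgement can be verified at source. On that view the sections need clearer cross-reference and nothing more. The high threshold and the documentation do limit the loss. They do not remove the conflict: Sections 11.1.1, 10.2.2 and 10.2.3 do not mention an exception, and no criteria for definite progression are given.

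Four further objections have weight:

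- **A reader might infer that withheld events never reach the database and cannot be recovered.** The protocol does not support this. Sections 10.2.2 and 10.2.3 send all examination findings to the CRF at every office visit, and Table 2 schedules visual acuity, IOP and concomitant treatments at least every 6 months. What is lost is the coded adverse event and its place in the incidence tables.
- **A reader might infer that the rule removes non-serious retinal ischaemia and vitreous haemorrhage as event types.** It does not. It reaches only cases firmly attributed to progression. A procedural complication is not progression, and many detachments or severe haemorrhages could meet the seriousness criteria and stay reportable.
- **Retinal ischaemia is not in the Section 12.5 sentence on adverse events to be tabulated.** The protocol says only that information on it will be evaluated. That is correct, but Section 12.5 also tabulates every individual adverse event, and a withheld case would be absent there.
- **The percentages are assumed.** This is also correct. They show direction and sensitivity, not an expected loss.

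**Conclusion.** The contradiction is real and rests on the text alone. For a non-serious event judged definitely due to disease progression, Section 11.4 gives an instruction that cannot be reconciled with Sections 11.1.1, 10.2.2 and 10.2.3. If Section 11.4 is followed, the adverse event tables under-count such events. If sites differ over which rule to follow, the counts are not comparable across sites.

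The size cannot be derived from the protocol, because the share of events so attributed is not given. The drop in detection probability to between 71.0% and 56.2% holds only under an assumed 25% to 50% share and an event type that is wholly non-serious. The sample size statement in Section 12.1 is not in error on this account. The point merits correction, but it does not show that the registry would fail to capture these events at all.

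**What to change.** Amend Section 11.4 to agree with Sections 11.1.1, 10.2.2 and 10.2.3:

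1. Record as adverse events, whatever the attribution, post-treatment retinal ischaemia, vitreous haemorrhage, retinal tear or detachment, vitreous detachment, and significant worsening of retinal disease.
2. Add a CRF field stating whether the investigator attributes the event to disease progression.
3. Tabulate these events with and without the flagged cases.
4. State whether the exception for serious events in Section 11.4 also covers the ocular surgery criterion in Section 11.3.2.

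Infections and IOP- or cataract-related events need no special provision here, since nothing in the protocol suggests that they would be taken for progression.

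The cost is a short amendment, a field on the adverse event form (the CRF itself is not at hand) and guidance to sites. The downside is more non-serious events to enter and somewhat higher reported rates. The second tabulation lets the sponsor show how much of that is attributed to progression. The change concerns data capture only and does not touch patient care.
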